^a Screening and Baseline visits can be on the same day only if *all* eligibility criteria are met and *all* required Screening and Day 1/Baseline tests and tasks are completed on the same day.

^b Except for the Day 28, 35, or 42 visits, if violations of treatment site restrictions prior to the visit are reported, details of the violation should be recorded in the CRF and the visit should be completed including evaluations and sampling.

^c On Baseline/Day 1, local tolerability is to be assessed 30-minutes after application of test articles.

For the Day 28, 35, and 42 Visits:

If violations of treatment site restrictions reported occurred more than 24 hours prior to the visit at the Day 28, 35, or 42 visits, details of the violation should be recorded in the CRF and the evaluations and sampling completed as scheduled.

If violations of treatment site restrictions less than 24 hours prior to the visit is reported at the Day 28, 35, or 42 visits, details of the violation should be recorded in the CRF. Evaluations can be completed but an additional visit 24-48 hours after the violation should be scheduled for sample collections.

Details on sampling sites are in Table 2 and the Collection Sampling, Storage, Shipping Procedure, provided separately.

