4.2.2 Secondary Endpoints

In the *S. aureus* MITT population, comparison of sites treated with DBI-001 or Aqueous Gel on the following microbial metrics:

- Change from baseline in abundance of *S. aureus* based on molecular diagnostic qPCR and CFU counts on samples obtained from treatment sites at days 7, 14, 21, 28, 35, and 42.
- Abundance of based on qPCR and CFU counts.
- Changes in the abundance and diversity of the microbiome as determined by 16s and/or whole genome sequencing.
- The proportion of subjects with a greater decrease in ADSI for the DBI-001-treated site than the Aqueous Gel-treated site.
- Change from baseline in signs and symptoms of local tolerability (pruritus, erythema, exudation, excoriation, and lichenification as well as pain, burning, or stinging) for the DBI-001-treated lesion and the Aqueous Gel-treated lesion.

INVESTIGATIONAL PRODUCT (IP)

Investigational Product and Aqueous Gel (Test Articles)

Test articles	Doses per Subject
1mL vial contains DBI-001 Gel with 10 ⁷ -10 ⁹ CFU / mL of	27 doses (once daily for 4 weeks)

ELIGIBILTY CRITERIA

Inclusion Criteria

Subjects must meet all of the following criteria to be included in the study:

1. Ability to understand, agree to, and sign the study Informed Consent. If the subject is unable to provide consent for him/herself, the subject's legally authorized representative may provide written consent.

2. A signed Health Information Portability and Accountability Act (HIPAA) authorization form which permits the use and disclosure of subject's individually identifiable health information.

3. Male or Female Subjects of any race 12-65 years of age.

4. Physician diagnosed clinically stable AD according to the criteria of Hanifin and Rajka with comparable anatomically symmetrical, bilateral target lesions (Hanifin and Rajka 1980). Each lesion must have an Atopic Dermatitis Severity Index (ADSI) score of ≥ 6 . It will be in the

opinion of the Investigator based on subject's medical history whether the lesions are clinically stable.

5. Female subjects of child-bearing potential must use at least one method of birth control that results in a low failure rate (i.e., less than 3 % per year) when used consistently and correctly such as implants, injectables, combined oral contraceptives, some intrauterine devices (IUDs), sexual abstinence or vasectomized partner for the duration of study participation.

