6.5.2 All Other Visits

Study visit assessments and sample collections will be conducted as presented in Tables 2 and 3.

The Screening and Day 1/Baseline visit can be combined for subjects meeting *all* eligibility requirements and only if *all* Screening and Day 1/Baseline tests and tasks can be completed on the same day.

Day 1/Baseline visit:

- 1. Confirm compliance with treatment site restrictions.
- 2. Record any changes in concomitant medications.
- 3. Record adverse event, if any.
- 4. Blinded evaluating investigator complete clinical assessment of severity of signs and symptoms of AD prior to application of test article.
- 5. Calculate ADSI score of both potential treatment sites if the Screening visit was on an earlier date. At Baseline, if ADSI eligibility criterion is no longer met, the subject is to be withdrawn from the study prior to sample collection and test article application.
- 6. Digital images of both treatment sites.
- 7. Collect PBS swabs from both treatment sites.
- 8. Collect samples from both treatment sites.
- 9. Unblinded treating investigator, or designee, to train subjects and/or LAR on method for selfor LAR to apply with a training vial.
- 10. Unblinded treating investigator, or designee, apply test articles after all evaluations and sampling have been completed.
- 11. Blinded evaluating investigator complete clinical assessment of local tolerability (severity pain, burning, or stinging in addition to pruritus, erythema, exudation, excoriation, and lichenification) 30-minutes after application of test articles to both treatment sites.
- 12. Review treatment site restrictions.
- 13. Review procedures for telemed visits.
- 14. Dispense 1% hydrocortisone ointment as needed.
- 15. Schedule appointment for Day 7 clinic visit and telemed visits.

Detailed instructions for sample collection, storage, and shipping are in the Collection Sampling, Storage, Shipping Procedure (CSSSP) provided separately. If violations of treatment site restrictions prior to the visit are reported details of the violation should be recorded in the CRF and the visit should be completed including evaluations and sampling.

DermBiont

Day 7 (±2)

- 1. Confirm compliance with treatment site restrictions.
- 2. Record any changes in concomitant medications.
- 3. Record adverse event, if any.
- 4. Blinded evaluating investigator complete clinical assessment of severity of signs and symptoms of AD.

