6.6.1 Grading of signs and symptoms of AD using ADSI

Both targeted treatment areas will be evaluated using the ADSI. The ADSI score represents the sum of the individual severity scores on none, mild, moderate, or severe for the following component signs and symptoms: erythema, pruritus, exudation, excoriation and lichenification. The investigators will only be required to calculate the ADSI at the Screening and Baseline visits to confirm that the subjects meet the inclusion criteria for disease severity. The ADSI for subsequent visits will be calculated during data analysis. The same observer-blinded investigator should perform the ADSI grading for each subject for the duration of a subject's participation in the study.

The same signs and symptoms of AD are also commonly use to evaluate application site reactions to topical product and serves a secondary role in characterizing tolerability. The sponsor will consider improvement in the ADSI and the individual signs and symptoms of AD an indicator of either a favorable therapeutic effect or the demonstration of the natural variation of AD over time. If the signs and symptoms increase in severity, the sponsor will consider this an indication of an application site reaction and/or the natural variation in AD over time. To further characterize local tolerability, subject self-reporting of pain, burning, or stinging will also be recorded. Each component is measured using the following scale:

Erythema score: (redness presents specifically in the target lesion)

0=none	No redness
1=mild	Mildly detectable erythema; pink
2=moderate	Dull red; clearly distinguishable
3=severe	Deep, dark red; marked and extensive

Exudation score: (oozing or crusting of the target lesion)

0=none	No oozing or crusting
1=mild	Minor or faint signs of oozing
2=moderate	Definite oozing or crusting present
3=severe	Marked and extensive oozing or crusting present

Excoriation score: (evidence of scratching in the target lesion)

0=none	No evidence of excoriation
1=mild	Slight excoriation present

2=moderate	Definite excoriation present
3=severe	Marked, deep, or extensive excoriation present

Pruritus: as reported by the subject as being the greatest intensity they have experienced within the last 24 hours at Baseline or since the last visit at subsequent visits.

0	None	No pruritus
1	Mild	Slight pruritus, not really bothersome
2	Moderate	Definite pruritus that is somewhat bothersome

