6.6.2 Local Tolerability

Tolerability will be evaluated based on calculating the scores for pruritus, erythema, exudation, excoriation, lichenification and the additional symptoms of pain, burning, or stinging using the following scale:

Pain, Burning, or Stinging: as reported by the subject as being the greatest intensity they have experienced within the last 24 hours at Baseline or since the last visit at subsequent visits.

0	None	No pain, burning, or stinging
1	Mild	Slight pain, burning or stinging sensation; not really bothersome
2	Moderate	Definite pain, burning or stinging that is somewhat
		bothersome
3	Severe	Significant pain, burning, or stinging sensation that causes definite
		discomfort and may interrupt daily activities and/or sleep.

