6.6.3 Sample Collection

Samples for microbiologic testing will be obtained separately from both treatment targeted sites as detailed in Table 2 below. Details of sample collection, storge, and shipment can be found in the CSSSP.

Visit	Sample	Test
Screening	None	
Day 1 (Baseline - Prior to Application)	1 Swab and 12 tape sample	qPCR Bacterial Culture S. aureus CFU
Day 7	1 Swab from each treatment site	qPCR Bacterial Culture S. aureus CFU
Day 14	1 Swab from each treatment site	qPCR Bacterial Culture S. aureus CFU
Day 21	1 Swab from each treatment site	qPCR Bacterial Culture S. aureus CFU
Day 28	1 Swab and 12 tape sample	qPCR Bacterial Culture S. aureus CFU
Day 35	1 Swab from each treatment site	qPCR Bacterial Culture S. aureus CFU
Day 42	1 Swab from each treatment site	qPCR Bacterial Culture S. aureus CFU

If the atopic dermatitis has cleared completely in a treatment site, the investigator is to use clinical judgment, anatomical landmarks and previously captured digital images to identify the specific location to be sampled.

Test Article Administration

All subjects will have approximately 27 applications of the assigned test articles applied to each treatment site by unblinded study personnel at the Day 1/Baseline, Day 7, Day 14 and Day 21 visits. Doses between visits will be applied by the subjects, or LAR, under the supervision of an unblinded treating investigator, or designee, during telemed visits on weekdays and unsupervised on weekends. Details of test article preparation are in the Pharmacy Instruction Manual, provided

separately. Approximately 0.1 ml of assigned test article will be applied to each treatment site (each site is approximately 100 cm^2). The product is to be air dried.

If technical or other logistical issues prevent a telemed connection (i.e., a weekday telemed is missed for any reason) the subject is to apply test articles unsupervised.

Concomitant medication and Excluded Therapy

Usage of prescription or over the counter topical or systemic medications will be reported during the subject's participation in the study. Subjects will be supplied with 1% Hydrocortisone Ointment to treat areas of A remote from the designated treatment sites.

Randomization

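### Pruritus in the ADSI is a 24-hour peak at Baseline but a since-last-visit peak afterwards, so per-side change from baseline is not like for like; the paired comparison is unbiased under no effect

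*Combined protocol and SAP*

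**What the plan says.** Section 6.6.1 builds the ADSI as the sum of five items, each scored 0 to 3: erythema, pruritus, exudation, excoriation and lichenification. Pruritus is the subject's report of the "greatest intensity they have experienced within the last 24 hours at Baseline or since the last visit at subsequent visits". Section 6.6.2 applies the same rule to pain, burning or stinging ("within the last 24 hours at Baseline or since the last visit at subsequent visits").

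Section 4.2.1 names change from baseline in ADSI and in its components as the primary endpoint, framed as a comparison of the two sites. Section 7.2.1 tests the between-side difference in ADSI change with a two-sided Wilcoxon signed rank test at each of Days 7, 14, 21, 28, 35 and 42. Section 7.3.1 summarises tolerability, pruritus included, as changes from baseline. If scores rise, section 6.6.1 says "the sponsor will consider this an indication of an application site reaction and/or the natural variation in AD over time".

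Entry selects on the same score. Inclusion criterion 4 says "Each lesion must have an Atopic Dermatitis Severity Index (ADSI) score of" 6 or more, and section 6.5.2 adds: "At Baseline, if ADSI eligibility criterion is no longer met, the subject is to be withdrawn from the study".

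At Day 1 the blinded evaluator grades the signs and symptoms of AD before application (section 6.5.2, item 4). All tolerability items, pruritus among them, are then graded "30-minutes after application of test articles to both treatment sites" (item 11). Table 1, footnote c, agrees: "On Baseline/Day 1, local tolerability is to be assessed 30-minutes after application of test articles".

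Under Test Article Administration, home doses are applied "during telemed visits on weekdays and unsupervised on weekends".

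**The concern.** A change score assumes that the same quantity is measured twice. Here the first value is a peak over one day and the second a peak over a period that may be several times longer. When a longer window contains the last 24 hours, its maximum cannot be lower than the 24-hour maximum, and it is higher whenever an earlier day was worse. Nothing in the supplied text aligns the windows or allows for the difference.

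At stake is the reading of each side on its own. A side with unchanged itch can appear to worsen, and a side with real benefit can appear flat. A rise would then be attributed under section 6.6.1 to an application site reaction and/or natural variation. Because the interval between visits varies, the shift also varies over time, which distorts the per-side time course. Pruritus matters to this programme: section 1.2 says that improvement in the pilot trial was most noticeable in pruritus.

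**Working it through.** The plan gives no figure on this point, so there is none to reproduce. The sample size rests on clinical judgement, with no SD or effect size.

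**1. Weight of the item.** Five items of 0 to 3 give an ADSI range of 0 to 15. Pruritus carries 3 of 15 points, and a shift of x points in pruritus is a shift of x points in ADSI. The other four items are lesion signs with no recall window.

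**2. Length of the later window, if visit means clinic visit.**
- Day 7 (±2): 5 − 1 = 4 to 9 − 1 = 8 days.
- Days 14, 21, 28 (±2): for example 12 − 9 = 3 to 16 − 5 = 11 days.
- Day 35: 31 − 30 = 1 to 39 − 26 = 13 days with ±4; 33 − 30 = 3 to 37 − 26 = 11 days with the ±2 in Table 1.
- Day 42: up to 46 − 31 = 15 days with ±4 at both visits. The Synopsis endpoints, and the component endpoint in section 4.2.1, give ±2 at Day 42. The longest gap is then 44 − 31 = 13 days.

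If weekday telemedicine calls count as visits, the on-treatment window is about 1 day, or 3 after a weekend. Dosing stops before the Day 28 visit and only clinic visits are booked afterwards, so Days 35 and 42 keep the long window on either reading.

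**3. Exact illustration with independent days and no true change.** For a daily 0–3 score with distribution function F, the expected peak over L days is 3 − [F(0)^L + F(1)^L + F(2)^L]. Assume daily probabilities 0.15, 0.35, 0.35, 0.15, so F = 0.15, 0.50, 0.85.
- L = 1: 3 − 1.50 = 1.50.
- L = 7: 3 − (0.000 + 0.008 + 0.321) = 2.67, a shift of +1.17.

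With assumed daily means of 1.9 and 2.4 the 7-day shifts are +0.97 and +0.59; the last is limited by the ceiling of 3. Independent days are an extreme case, because itch on neighbouring days is likely to be correlated.

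**4. Correlated days, stable disease, 7-day window (simulation).**
- Model A: autoregressive latent itch, mean 1.6, day-to-day correlation 0.3–0.9, no entry filter. Per-side pruritus change is +0.18 to +0.70, against 0.00 with matched windows.
- Model B: grades cut from a latent normal, daily mean 1.5–2.4, correlation 0.5–0.95, only subjects with ADSI of 6 or more on both sides kept. The window alone adds +0.12 to +0.83. Other windows add 0.00 (1 day), +0.09 to +0.53 (3 days) and +0.15 to +1.02 (15 days).
- A similar model without the entry filter gives +0.26 to +1.03.

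Together this is roughly +0.1 to +1.0 points per side.

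**5. Net ADSI change.** Selection at entry pulls the other way. In Model B the stable per-side ADSI change is −0.54 to −0.02 with matched 24-hour windows and −0.16 to +0.75 with the 7-day peak.

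**6. Between-side pruritus difference.** Under no effect it is 0.00 with either window. Under a true effect:

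| Setting | 24 h at both | Peak |
|---|---|---|
| Model A, 0.5-point effect | −0.46 to −0.49 | −0.45 to −0.49 |
| Model B, mean 1.5–1.7 | −0.58 to −0.64 | −0.46 to −0.63 |
| Model B, mean 2.0 | −0.53 to −0.58 | −0.35 to −0.54 |
| Model B, mean 2.4 | −0.44 to −0.53 | −0.16 to −0.46 |
| Model B, Day 7, benefit complete by Day 7 | −0.53 to −0.64 | −0.16 to −0.29 |

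At mean 2.0, pairing the weakest ends gives 1 − 0.35/0.53 = 0.34, a loss of up to about a third. At mean 1.5 the standardised effect hardly moves (0.60–0.94 versus 0.59–0.93).

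**7. One case showing both results** (Model A, correlation 0.6, within-subject SD 0.6, 0.5-point benefit). With matched windows the active and control sides change by −0.46 and 0.00. With the documented windows they change by +0.14 and +0.60. The active side seems to worsen, yet the difference is 0.14 − 0.60 = −0.46, unchanged.

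**The case against.** The strongest reply is that the named endpoints and the primary test are between-side and both sides of a subject share each window, so the shift cancels. P-values are, moreover, mainly exploratory. This stands under no effect. A reader might infer a false-positive bias in the primary test; the documents do not support that. Under a true effect the cancellation is only partial in some settings. Dilution is not confined to the ceiling, since it already appears at mean itch 2.0, but Model A shows almost none, so no firm figure can be given.

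A reader might also infer that ADSI will worsen on both sides. That does not follow. Telemedicine calls may count as visits, and selection on ADSI of 6 or more can leave the net change negative.

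The rule for reading a rise does include natural variation, and a higher peak from ordinary fluctuation is a form of it. The rule is therefore not plainly wrong, but it cannot separate a longer window from a change in disease.

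For the tolerability summary the direction is not known at all. Pruritus, like pain, burning or stinging, is scored 30 minutes after the first application, so that value may already contain a reaction. The plan does not say which Baseline pruritus score the summary uses.

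Finally, a since-last-visit peak has a purpose: it catches flares and reactions between visits. That supports keeping it as a separate item; it does not support subtracting a 24-hour baseline from it.

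**Conclusion.** The mismatch is certain from the text. Relative to matched windows, and if visit means clinic visit, it moves per-side change in pruritus and ADSI toward worsening whenever itch fluctuates below 3. It adds nothing when itch is constant or already at 3. The size, roughly +0.1 to +1.0 points per side for a 7-day window, rests on assumed itch distributions and perfect recall of the peak. It indicates scale and is not an estimate for this trial.

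The primary paired comparison is unbiased under no effect. Under a true effect, the loss in the pruritus difference ranges from little at mean itch about 1.5 to up to about a third at mean 2.0. It is larger near the ceiling, and at Day 7 if benefit builds over the window (an assumption). The harm falls mainly on the descriptive per-side and tolerability summaries. Severity is low to moderate, and the change is worth making because it is cheap.

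**What to change.** - Use one fixed recall window at Baseline and every later visit for pruritus within ADSI and for pain, burning or stinging. The Baseline window is already 24 hours.
- Record worst-since-last-visit as a separate safety item outside ADSI, and state whether visit means clinic visit.
- Use the pre-application pruritus score, and add a pre-application pain, burning or stinging score, as the tolerability baselines. Report the 30-minute scores separately.
- Reconcile the visit windows at Day 35 (±2 and ±4) and Day 42 (±2 and ±4).

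The cost is protocol and CRF wording, one extra safety item per visit and one extra question at Baseline. There are two downsides. Flares between visits leave ADSI, though the separate item keeps them. A one-day score may also be slightly noisier: in Model B the SD of the side difference in pruritus change was 0.60–1.00 (24 h) against 0.59–0.90 (peak), and the SD for ADSI rose by at most 6%.

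If data are already collected, state the mismatch in the SAP and base efficacy conclusions on pruritus and ADSI on the between-side difference. For tolerability, still report absolute per-side severity at each visit, because irritation common to both gels cancels in the side difference and would otherwise be hidden.

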6.6.2 Local Tolerability

Tolerability will be evaluated based on calculating the scores for pruritus, erythema, exudation, excoriation, lichenification and the additional symptoms of pain, burning, or stinging using the following scale:

Pain, Burning, or Stinging: as reported by the subject as being the greatest intensity they have experienced within the last 24 hours at Baseline or since the last visit at subsequent visits.

0	None	No pain, burning, or stinging
1	Mild	Slight pain, burning or stinging sensation; not really bothersome
2	Moderate	Definite pain, burning or stinging that is somewhat
		bothersome
3	Severe	Significant pain, burning, or stinging sensation that causes definite
		discomfort and may interrupt daily activities and/or sleep.

6.6.3 Sample Collection

Samples for microbiologic testing will be obtained separately from both treatment targeted sites as detailed in Table 2 below. Details of sample collection, storge, and shipment can be found in the CSSSP.

Visit	Sample	Test
Screening	None	
Day 1 (Baseline - Prior to Application)	1 Swab and 12 tape sample	qPCR Bacterial Culture S. aureus CFU
Day 7	1 Swab from each treatment site	qPCR Bacterial Culture S. aureus CFU
Day 14	1 Swab from each treatment site	qPCR Bacterial Culture S. aureus CFU
Day 21	1 Swab from each treatment site	qPCR Bacterial Culture S. aureus CFU
Day 28	1 Swab and 12 tape sample	qPCR Bacterial Culture S. aureus CFU
Day 35	1 Swab from each treatment site	qPCR Bacterial Culture S. aureus CFU
Day 42	1 Swab from each treatment site	qPCR Bacterial Culture S. aureus CFU

If the atopic dermatitis has cleared completely in a treatment site, the investigator is to use clinical judgment, anatomical landmarks and previously captured digital images to identify the specific location to be sampled.

Test Article Administration

All subjects will have approximately 27 applications of the assigned test articles applied to each treatment site by unblinded study personnel at the Day 1/Baseline, Day 7, Day 14 and Day 21 visits. Doses between visits will be applied by the subjects, or LAR, under the supervision of an unblinded treating investigator, or designee, during telemed visits on weekdays and unsupervised on weekends. Details of test article preparation are in the Pharmacy Instruction Manual, provided

separately. Approximately 0.1 ml of assigned test article will be applied to each treatment site (each site is approximately 100 cm^2). The product is to be air dried.

If technical or other logistical issues prevent a telemed connection (i.e., a weekday telemed is missed for any reason) the subject is to apply test articles unsupervised.

Concomitant medication and Excluded Therapy

Usage of prescription or over the counter topical or systemic medications will be reported during the subject's participation in the study. Subjects will be supplied with 1% Hydrocortisone Ointment to treat areas of A remote from the designated treatment sites.

Randomization

Each enrolled subject will be randomized to a test article kit number containing two different vials of test articles for each scheduled application. Each kit will contain vials labelled with "Right" or "Left", indicating the treatment side to apply onto. Treatment compliance will be monitored by recording all missed doses in source documentation and the CRF.

DATA ANALYSIS AND STATISTICAL CONSIDERATION.

General Statistical Considerations

All statistical processing will be performed using Statistical Analysis System (SAS®) unless otherwise stated. No interim analyses are planned. Except where noted, all statistical tests will be two-sided and will be performed at the 0.05 level of significance. P-values will be provided primarily for exploratory purposes.

Descriptive statistics will be used to provide an overview of the efficacy and safety results. For categorical parameters, the number and percentage of subjects in each category will be presented. For continuous parameters, descriptive statistics will include the number of subjects, mean, and standard deviation, median, minimum, and maximum. Appropriate inferential statistics will be used for the primary and secondary efficacy variables in an exploratory manner.

Linear interpolation of efficacy variables will be performed using observed data that precedes and follows the off-schedule visit, if present. The last observation will be carried forward if all the data subsequent to the off-schedule value is missing.

No adjustments will be made for multiplicity.

DermBiont

The number of subjects in each analysis set will be summarized. Reasons for study withdrawal will be summarized using frequencies and percentages by treatment group.

Reported AEs, medical history terms and prior and concomitant procedures and therapies will be classified on the basis of the f Medical Dictionary for Regulatory Activities (MedDRA) terminology. Prior and concomitant medications will be classified on the basis of the World Health Organization Drug Dictionary (WHO-DDE) terminology.

A statistical analysis plan (SAP), describing all statistical analyses will be provided as a separate document. The SAP will be finalized prior to unblinding of the study treatments.

Analysis of Efficacy Data for Objectives

7.2.1 Primary Efficacy:

The primary analysis will compare the differences from baseline in ADSI score between DBI-001 and Aqueous Gel will be done using a two-sided Wilcoxon sign rank test at each of Days 7, 14, 21, 28, 35 and 42.

The proportion of subjects with a greater decrease in ADSI for the DBI-001-treated lesion than the Aqueous Gel-treated lesion will be summarized descriptively for Days 7, 14, 21, 28, 35, and 42.

Comparison of differences at Day 28 between DBI-001 and Aqueous Gel of abundance of on lesioned skin will be done using a two-sided Wilcoxon sign rank test.

Comparison of differences at Day 28 between DBI-001 and Aqueous Gel of abundance and diversity of the microbiome based on DNA sequencing will be done using a two-sided Wilcoxon sign rank test.

Comparisons at Days 7, 14, 21, 35, and 42 will also be done. Additionally, a repeated measures model will be used to compare DBI-001 to Aqueous Gel for the secondary endpoints. P-values will be provided for descriptive purposes.

7.2.2 Secondary Efficacy:

The secondary analysis of the S. aureus MITT population will compare the differences at Day 28 between DBI-001 DP and Aqueous Gel in abundance of *S. aureus* based on qPCR using a 2-sided Wilcoxon sign rank test, alpha = 0.05, with a null hypothesis of median difference equal to zero.

Comparisons at Days 7, 14, 21, and 35 will also be done. Additionally, a repeated measures model will be used to compare DBI-001 DP to Aqueous Gel for the secondary endpoints. P-values will be provided for descriptive purposes.

7.2.3 Exploratory Efficacy:

Comparison in changes in the overall microbiome as defined by whole genome sequencing of samples obtained prior to, during, and after treatment.

Comparison of change from baseline in individual signs and symptoms of AD (components of ADSI score) between DBI-001 DP and Aqueous Gel will be done using a two-sided sign test at each of Days 7, 14, 21, 28, 35, and 42.

Additionally, a repeated measures model will be used to compare DBI-001 DP to Aqueous Gel for the above exploratory endpoints.

